1 INTRODUCTION

CooperVision, Inc. (CVI) is aiming to compare subjective ratings of lens handling at insertion of two CooperVision lenses: clariti elite versus Proclear 1 day in habitual soft lens wearers. The clariti elite lens will be considered an investigational lens in this study (as this frequent replacement monthly lens is not yet commercially available in Canada), the Proclear 1 day is commercially available in Canada.

Most soft contact lenses are worn on a daily wear basis, requiring that lenses are inserted at the beginning of the wear day and removed at night. A large variety of contact lenses are currently available on the market, each with different lens properties. These properties are influenced by the lens material composition and other factors, such as whether the lens is a re-usable contact lens or daily disposable contact lens. Differences between lenses include the stiffness of the material, a handling tint, indicators for telling the user whether the lens is inside-out, and whether the lens retains its shape on the finger during placement on eye. These varying properties can largely affect the ease of handling at insertion and removal, contributing to lens success or failure.

The clariti elite lens is a monthly replacement, silicone hydrogel lens without a handling tint. The Proclear 1 Day lens is a daily disposable, hydrogel lens with a handling tint. Both lenses have unique material characteristics.

CooperVision, Inc. is interested in comparing subjective handling acceptance, specifically lens handling at insertion between these two lenses of different materials to gain insight into the differences between these lenses from this aspect.

2 OBJECTIVES

The objective of this investigation is to evaluate subjective ratings of lens handling at insertion, specifically subjective rating of the ease of lens application to eye by participants for two CooperVision lenses, clariti elite versus Proclear 1 day, in habitual soft lens wearers.

The primary outcome variable for this study is:

- Subjective rating of ease of lens application to eye (0-100, integer steps)

The other outcome variable for this study is:

- [REDACTED]

[figure not shown]
3 HYPOTHESIS

The study null hypothesis is that the subjective rating of ease of lens application to eye for clariti elite will not be different from Proclear 1 Day lenses.

4 MATERIALS AND METHODS

4.1 STUDY DESIGN

4.1.1 OVERALL DESIGN

Participants will attend a screening visit to determine their eligibility for the study (Visit 1). Eligible participants continue in the study visits right after the screening visit on the same day and wear the study lenses bilaterally in randomized order.

Participants will complete subjective ratings using a numeric rating scale (0-100) at each visit and a Likert scale for handling related to lens insertion and overall handling experience at the end of the study. The subjective ratings will be reviewed by the investigator at the respective visits.

4.1.2 STUDY DURATION

All visits will be conducted on the same day, in sequential order. Estimated duration of involvement for each participant is 4hrs. The duration of this study from start of enrolment to the end of final appointment is expected to be approximately 5 weeks, with the enrolment period lasting approximately 4 weeks.

4.1.3 RANDOMIZATION

Considering the bilateral cross-over study design, participants will either wear Proclear 1 day or clariti elite lenses in both eyes first and then switch over to the alternate lens type. The order of lenses will be determined using a randomization schedule.

A randomization schedule will be generated for the study by CORE's data management team and provided to the research assistants. Study investigators will remain masked to the randomization schedule until the study is completed and the database is locked.

4.1.4 MASKING

[figure not shown]
This is a double-masked study. Both participants and investigators will be masked to the lens assignment.

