4.3.5 CONTACT LENS DISPENSING - MASKED

For the purpose of masking of participants and investigators, lenses will be over-labelled prior to dispense (based on the randomization assignment) by the study research assistant/unmasked personnel.

At study visits, lenses will be provided to participants in over-labelled blister packs to facilitate masking of participants and investigators. The use of saline for rinsing the contact lens prior to insertion is permitted if necessary. Saline will not be dispensed during the study.

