4.4.3 LENS 1 WEAR PERIOD (V2)

The Screening Visit (V1) will be immediately followed by Lens 1 Wear Period (V2) on the same day.

Visit procedures:

1. Participant will be assigned a randomization ID (by the study research assistant/unmasked staff)
2. Lens pair #1 will be provided to participants in a manner, which does not unmask the participant or investigator, as described in Section 4.3.5.
3. Participant to open blister packs and apply the Lens pair 1 OU – [REDACTED]
[REDACTED]
4. The participant will be asked to provide binocular subjective ratings at insertion for the following (0-100, integer steps):
 - i) Ease of blister pack opening
 - ii) CL stability on fingertip
 - iii) Ease of CL application to eye
5. [REDACTED]
6. [REDACTED]
7. [REDACTED]
8. [REDACTED]
9. [REDACTED]
10. [REDACTED]
11. [REDACTED]
12. [REDACTED]
13. The participant will remove the lenses.

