4.4.4 LENS 2 WEAR PERIOD (V3)

The Lens 1 Wear Period (V2) will be immediately followed by Lens 2 Wear Period (V3) on the same day. This visit will involve the alternate lens type, i.e. the study lens type not yet worn.

Visit procedures:

1. The participant will be assigned the second pair (lens pair #2) of study contact lenses, which will be selected according to the randomization table by unmasked study personnel.
2. The crossover lens pair #2 will be provided to participants in a manner, which does not unmask the participant or investigator, as described in Section 4.3.5.
3. Repeat steps 3-13 from V2 (section 4.4.3).
4. Subjective preference 5-point Likert between lenses for handling related to lens insertion/ removal and overall handling experience (binocular preference).

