4.6.12 QUESTIONNAIRES AND SUBJECTIVE RATINGS

Subjective ratings:

[figure not shown]
After lens insertion at visits 2 and 3, participants will be asked to complete questionnaires for binocular subjective ratings (0-100, integer steps) related to:

- i) Ease of blister pack opening,
- ii) Lens stability on fingertip
- iii) Ease of lens application to eye (key outcome)

At the end of visit 3 after removing lens pair 2, participant will be asked to complete a 5-point Likert preference questionnaire (to select one of the following answers for each question: prefer Lens pair #1 strongly, prefer Lens pair #1 slightly, No preference, prefer Lens pair #2 slightly, prefer Lens pair #2 strongly) binocularly related to:

- i) Overall lens handling at insertion
- ii) Overall lens handling at removal
- iii) Overall lens handling experience

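### Does the difference in handling tint between the two lenses undermine the claim that participants are masked?

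*Combined protocol and SAP*

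**What the plan says.** Section 4.1.4 claims masking of both parties without qualification in its visible text: "This is a double-masked study. Both participants and investigators will be masked to the lens assignment".

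Section 1 describes clariti elite as a monthly "silicone hydrogel lens without a handling tint. The Proclear 1 Day lens is a daily disposable, hydrogel lens with a handling tint". It also lists tint among the ways lenses differ ("Differences between lenses include the stiffness of the material, a handling tint, indicators for telling the user whether the lens is inside-out") and adds that "These varying properties can largely affect the ease of handling at insertion and removal".

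The means of masking are in section 4.3.5: "lenses will be provided to participants in over-labelled blister packs to facilitate masking of participants and investigators". The visit sections refer back to it. At V2 (section 4.4.3) the step is "Participant to open blister packs and apply the Lens pair 1 OU", and for V3 section 4.4.4 says that "The crossover lens pair #2 will be provided to participants in a manner, which does not unmask the participant or investigator". Section 4.6.12 sets the time of rating: "After lens insertion at visits 2 and 3, participants will be asked to complete questionnaires for binocular subjective ratings". The ratings include ease of application to the eye, the primary outcome in section 2. The preference form in section 4.6.12 identifies the lenses only as pair 1 and pair 2.

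**The concern.** An over-label hides the name on the pack. Once the pack is open it hides nothing about the lens. By the protocol's own account one lens is tinted and the other is not, and the same person handles both within a visit of about four hours. The visible text describes no step that conceals the tint.

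The primary outcome is a self-rating given straight after handling, so participant masking matters more here than investigator masking. If participants recognised a product and held an opinion of it, the opinion could enter the rating. Randomising the order would not remove this, because the expectation would belong to the product and not to the period. A reader who took the double-masked label at face value might then credit the result with protection that the procedures do not fully give.

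**Working it through.** **1. What is concealed and what is not**

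| Feature | Visible text | Concealed from the participant? |
|---|---|---|
| Product name on the pack | Over-labelled by unmasked staff (4.3.5) | Yes |
| Order of lenses | Schedule held by research assistants (4.1.3) | Yes |
| Name on the preference form | Pair numbers only (4.6.12) | Yes |
| Tint of the lens | Control tinted, test not (1) | No measure visible |

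The last row has limits. A figure in 4.1.4 is not shown in the public copy, and the text directly after the application step in 4.4.3 is blacked out. A further measure could stand in either place.

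**2. From tint to bias**

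Masking in 4.1.4 is to lens assignment, that is, to which product is worn in which period. For a tint difference to bias the rating, three things must hold:

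- The tint is noticeable on the finger. Its strength is not given, and Table 1 as shown has no tint row.
- The participant knows which product is the tinted one. The consent text is not public. Some habitual wearers may know Proclear 1 day, or the clariti 1 day lens that section 6 describes as essentially the same as the test lens, but the documents do not show how many.
- The participant expects one product to handle better. Nothing in the documents bears on this. Both lenses come from the same manufacturer (4.3.1).

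Seeing that pair 2 differs from pair 1 tells a crossover participant only what the design already implies. A tint that makes a lens easier to handle is a property of the product, and the study sets out to compare products.

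**3. What an expectation effect would do, if there were one**

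Inputs from section 4.2.1: SD of the paired difference 18, target difference 10, two-sided alpha 0.05, power 80%, target of 30 participants.

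The plan's own figure comes first. Power of the paired t-test is taken from the noncentral t distribution with n − 1 degrees of freedom and noncentrality (10/18)√n. At n = 27 it is 0.794 and at n = 28 it is 0.809, so the stated minimum of 28 is reproduced. At n = 30 it is 0.837.

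Now suppose no true difference and a mean shift of b points from expectation, with noncentrality b√30/18. The values of b are assumptions, since the documents give none.

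| Assumed shift b (points) | Noncentrality | Chance of a significant result |
|---|---|---|
| 0 | 0 | 0.05 |
| 1 | 0.30 | 0.06 |
| 2 | 0.61 | 0.09 |
| 3 | 0.91 | 0.14 |
| 5 | 1.52 | 0.31 |
| 10 | 3.04 | 0.84 |

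A shift of one or two points would do little; a shift of five or more would matter. Nothing in the documents places the trial on this scale.

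**4. What a change would buy**

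*Rewording 4.1.4.* The lenses, the ratings, the paired test and the estimate stay as they are. If an expectation effect exists, it is the same size afterwards.

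*Asking participants at exit which lens each pair was.* The exact (Clopper-Pearson) 95% interval for x of 30 runs from the 0.025 quantile of Beta(x, 31 − x) to the 0.975 quantile of Beta(x + 1, 30 − x):

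- 10 of 30: 17% to 53%
- 15 of 30: 31% to 69%
- 25 of 30: 65% to 94%

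Splitting the primary difference by the answer, with SD 18 assumed in each subgroup, gives a 95% half-width of t(0.975, 28) × 18 × √(1/a + 1/b), where a and b are here the subgroup sizes:

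- 15 and 15: 2.048 × 18 × 0.365 = 13.5 points
- 20 and 10: 2.048 × 18 × 0.387 = 14.3 points
- whole sample, for comparison: t(0.975, 29) × 18/√30 = 2.045 × 3.286 = 6.7 points

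Both subgroup half-widths exceed the 10-point target difference, so the split could not be used. A guess made after handling would also mix recognition with real handling differences.

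**The case for a change.** The strongest case for a change is that the protocol names a visible difference relevant to handling and then promises full participant masking without mentioning it. The visit sections cite only 4.3.5, whose visible text covers only the pack. The outcome is wholly subjective, and no objective measure in the visible text supports it. Correcting the description would cost a sentence. On this view it does not matter that no bias has been shown, because the description claims more than the procedure secures.

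Part of this stands. The visible measures protect the name and not the lens, and 4.1.4 is worded more firmly than 4.3.5, which says only that over-labelling helps masking. The report should not repeat the label without mentioning the tint.

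The argument goes no further than that. It shows that the pairs may be distinguishable, not that the assignment is known. The gaps in the public copy fall where a further measure would be described, so absence from the visible text is weak evidence of absence from the plan. The statement in section 1 that such properties affect handling describes a product effect, which the study is meant to capture.

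**Conclusion.** No change to the plan is needed. The tint is intrinsic to the marketed control lens, and a participant applying a lens normally sees it. Imperfect concealment is therefore a fair cost of comparing these two products on handling, and over-labelling removes the most direct cue, the product name. The suggested remedies change a description or add a count that could not alter the analysis. The sample size of 28, raised to 30, is sound on its own inputs and does not depend on this point.

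What is left is a minor wording matter that a sensible report author settles unprompted: note beside the masking description that only the control lens is tinted, and read the self-rating with that in mind if nothing conceals it.

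Confidence is moderate. The conclusion rests on two facts about the documents: they do not show that participants can identify the product, and they give no size or direction for any expectation effect. Evidence that participants were told which lens is tinted, or that many already wore one of the products, would strengthen the concern.

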4.2 STUDY POPULATION

4.2.1 SAMPLE SIZE CALCULATION

Sample size: The target sample size for this study is 30 participants to be randomized and to wear both lens types. This target was determined based on the sample size calculation below:

Based on previous data for "lens handling for removal" which showed a standard deviation of the difference between means of 18 points (0-100 scale), a minimum sample size of 28 is required to detect a paired difference between groups of 10 units on a 0-100 scale with 80% power and alpha 0.05 in a two-tailed t-test.

Therefore, in this study, a maximum of 30 participants to be randomized and wear both lens types.

11. Have undergone refractive error surgery or intraocular surgery;
12. Are a member of CORE directly involved in the study.

* For the purposes of this study, active ocular disease is defined as infection or inflammation which requires therapeutic treatment. Mild (i.e. not considered clinically relevant) lid abnormalities (blepharitis, meibomian gland dysfunction, papillae), corneal and conjunctival staining and dry eye are not considered active ocular disease. Neovascularization and corneal scars are the result of previous hypoxia, infection or inflammation and are therefore not active.

* Any potential exclusion will be reviewed with the Lead Investigator or Principal Investigator prior to final decision making.

4.2.4 REPEATED SCREENINGS

In some circumstances a repeated screening may need to be scheduled. The maximum total number of screenings permitted will be 2, i.e. 1 re-screen. Examples of reasons include, but are not limited to:

1. Incomplete information available at time of screening to determine eligibility (e.g. current lens brands worn, current mediation, etc.);
2. Study procedures unable to be completed in time scheduled for visit;
3. Study products not available at the time of the screening visit;
4. The short-term use of medications (e.g. antibiotics, antihistamines etc.);
5. Reassessment of baseline ocular conditions (e.g. corneal and/or conjunctival staining, scars etc.).

4.3 STUDY MATERIALS

4.3.1 LENSES

If deemed eligible after screening, participants will wear two different contact lenses bilaterally on the same day, in a randomized sequential order: clariti elite and Proclear 1 day.

The control lens is the commercially available, daily disposable Proclear 1 day, manufactured by CooperVision, Inc. The test lens is the frequent replacement (monthly) clariti elite, manufactured by CooperVision, Inc.

The test lenses are not approved for sale in Canada and therefore and ITA (Investigational Testing Authority) will be sought from Health Canada prior to them being used in the study. The control lens, Proclear 1 day, is commercially available in Canada.

Lenses will be worn for a period of approximately 90 minutes each during the study visit only.

Table 1: Study lens specifications

	Test	Control
Lens name	clariti elite	Proclear 1 day
Manufacturer	CooperVision	CooperVision
HC licence #	N/A- investigational	106827
Material	somofilcon A	omafilcon A
EWC (%)	56%	60%
Dk/t (-3.00)	86	28
Base Curve (mm)	8.6	8.7
Diameter (mm)	14.2	14.2
Sphere Power (D)	-1.00 to -6.00 (0.25 steps)	-1.00 to -6.00 (0.25 steps)
Replacement schedule	Monthly replacement	Daily disposable

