4.4 SCHEDULED AND UNSCHEDULED VISITS

4.4.1 STUDY VISITS

All visits will be conducted subsequent to each other, on the same day. Estimated on-site visit time and duration of involvement for each participant is 4hrs. A summary of the visit codes and duration are listed in Table 2 below.

Table 2: Summary of visits

Visit number	Visits	Visit length
1	Screening	1.0 hrs
2	CL Pair 1 wearing period	1.25 hr
3	CL Pair 2 wearing period	1.5 hr
4	End of study visit and Study Exit	0.25 hr
Total		4 hrs

[figure not shown]

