6 POTENTIAL RISKS AND BENEFITS TO HUMAN PARTICIPANTS

Due to the short-term, daily wear nature of the study, this study is considered a non-significant risk study based on International Standards Organization (ISO) guidelines. This is a higher than minimal risk study according to Health Canada because of the use of non-marketed products. The study assessments are all non-invasive, standard optometric assessments.

The investigational contact lenses used in this study are silicone hydrogel lenses, worn on a daily wear basis, with a monthly replacement frequency. Whilst this lens is not marketed in Canada, it is essentially the same as the clariti 1 day lens, which is marketed in Canada. It is also commercially available in the United Kingdom.

Each of the 2 lens types will be worn for approximately 90 minutes during the day, closely monitored by the investigator.

When contact lenses are worn on a daily wear basis there is a small risk of an adverse event compared to not wearing contact lenses. When contact lenses are worn on an extended wear basis, there is a significantly increased risk of an adverse reaction compared with wearing contact lenses on a daily wear basis.

Adverse events and/ or complications of daily wear of soft contact lenses can occur (e.g. inflammation and infection). Complications that may occur during contact lens wear include discomfort, dryness, burning, excessive tearing, aching or itching eyes, discharge, hyperemia and variable, cloudy or blurred vision. Other non-serious contact lens related complications include peripheral ulcers, papillary conjunctivitis, superior epithelial arcuate lesions, etc. More serious risks may include photophobia, iritis, corneal edema or eye infection. Although contact lens-related infections are very infrequent, the possibility does exist. The incidence of infection due to day-wear soft lenses is 0.035%. Almost always an infection will occur only in one eye. This risk is assumed by 3.5 million Canadians, 35 million Americans and more than 140 million people worldwide who wear contact lenses.

Fluorescein is used in this study to assess the ocular surface. Although rare, it is possible that participants may have an allergic reaction to the dye. They will be advised of the fluorescein use

in the consent document and will be instructed to advise the investigator if they have a known allergy to fluorescein.

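### Does the stated wear of about 90 minutes per lens conflict with the 75 minutes allotted to the first wearing visit in a way that matters?

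*Combined protocol and SAP*

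**What the plan says.** Two sections give the wear time. Section 4.3.1 says "Lenses will be worn for a period of approximately 90 minutes each during the study visit only", and Section 6, which describes risks and benefits, says "Each of the 2 lens types will be worn for approximately 90 minutes during the day, closely monitored by the investigator".

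Table 2 in Section 4.4.1 gives the visit lengths. Its rows for the two wearing visits read "CL Pair 1 wearing period 1.25 hr" and "CL Pair 2 wearing period 1.5 hr". Screening has 1.0 h and study exit 0.25 h. The text above the table reads "Estimated on-site visit time and duration of involvement for each participant is 4hrs", and Section 4.1.2 gives the same estimate.

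Section 4.4.3 sets out what happens in V2. Step 3 is "Participant to open blister packs and apply the Lens pair 1 OU". In step 4, "The participant will be asked to provide binocular subjective ratings at insertion". Step 13 is lens removal. Steps 5 to 12, and some text after step 3, are redacted. Section 4.4.4 says that V3 follows V2 at once and repeats steps 3 to 13 with the other lens. A preference questionnaire follows; Section 4.6.12 places it after the second pair is removed.

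**The concern.** The first pair goes on and comes off within V2, and V3 starts immediately afterwards. The redacted steps lie between insertion and removal, so they cannot supply wear time outside the visit. A 75-minute visit cannot hold 90 minutes of wear, let alone pack opening and insertion as well. V3 is tight too: 90 minutes of wear would fill the visit and leave nothing for insertion or the questionnaire.

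Three things could be at stake:

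- **Exposure.** The test lens is investigational in Canada, and Section 6 states the exposure participants will have. If Table 2 reflects practice, that statement is wrong for the first pair.
- **Participant time and payment.** If 90 minutes per lens is what happens, the estimated 4 hours is too short. Section 10 pays $20 per scheduled visit hour.
- **Deviations.** Section 14.4.3 requires every deviation to be documented. With two figures and no visible tolerance, it is unclear whether first-pair wear under 75 minutes counts as one.

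**Working it through.** **Inputs.** Wear of about 90 min per lens (Sections 4.3.1 and 6). Visit lengths from Table 2: V1 1.0 h = 60 min, V2 1.25 h = 75 min, V3 1.5 h = 90 min, V4 0.25 h = 15 min. Total 4 h (Sections 4.1.2 and 4.4.1).

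**The plan's own total.** 60 + 75 + 90 + 15 = 240 min = 4.0 h. Table 2 adds up, so the inconsistency is between sections and not within the table.

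**Time left in each visit after wear.** Time left = visit length − wear, before any handling time. The documents give no tolerance around 90, so 85 and 80 are assumed readings of an approximate 90.

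| Wear per lens | Left in V2 (75 min) | Left in V3 (90 min) | Both visits (165 min) | Total on site if each wearing visit equals the wear time |
|---|---|---|---|---|
| 90 min | −15 | 0 | 165 − 180 = −15 | 60 + 90 + 90 + 15 = 255 min (4.25 h) |
| 85 min | −10 | 5 | 165 − 170 = −5 | 60 + 85 + 85 + 15 = 245 min (4.08 h) |
| 80 min | −5 | 10 | 165 − 160 = 5 | 60 + 80 + 80 + 15 = 235 min (3.92 h) |

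The V2 shortfall appears on all three readings. At the nominal figure it is 15/90 = 17%. The shortfall over both visits does not hold throughout: the average room per lens is 165/2 = 82.5 min, so the combined wear fits at 80 min each and fails at 85.

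**Participant time and payment.** 255 − 240 = 15 min, which is 15/240 = 6% of the estimated 4 h. At $20 per hour this is 0.25 × 20 = $5 per participant.

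**The primary outcome.** Ease of application is rated at step 4, directly after insertion. In V2 it precedes any wear of consequence. In V3 it follows first-pair wear, but a short first wear belongs to the period and not to the lens, and Section 4.1.3 randomizes which lens comes first. The figure in dispute does not enter the sample size calculation (Section 4.2.1) or the paired comparison (Section 11.1, Table 6).

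**The preference questionnaire.** It comes after both wears. If first-pair wear were shorter, the difference would again follow period, with either lens able to be first.

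**The case for a change.** The strongest case for acting is that the V2 conflict survives every reasonable reading. Table 2 works in quarter-hours and still separates 1.25 from 1.5, so at its own precision the first visit is not 90 minutes. Wear time is also the exposure statement for an investigational lens, and correcting it would cost only wording.

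The contradiction itself stands. Its consequences are weaker than they look:

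- **Looseness of the figures.** The wear time is approximate in both places and the total is an estimate in both places. No section makes a visit length a limit, and a 75-minute slot can run over.
- **Different lengths for V2 and V3.** These are not in themselves a conflict, because V3 also holds the preference questionnaire.
- **Tolerance.** A timed wear instruction or window could sit in the redacted V2 steps, which site staff can read in full. That none exists cannot be established from the public text.
- **Deviations.** Section 14.4.2 classes timing departures that do not affect safety, efficacy or the design as minor and not reportable to the ethics office. Section 14.4.3 still requires them to be documented and sent to the sponsor, so what remains is paperwork.
- **Exposure.** If Table 2 is what happens, Section 6 overstates exposure. That errs on the cautious side and adds no risk.

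**Conclusion.** No change to the plan follows. Sections 4.3.1 and 6 disagree with Table 2 about the first pair: a nominal 90 minutes of wear against a ceiling of 75. This is a clerical slip between planning figures. Its largest visible effect is about 15 minutes (6%) on an estimated 4-hour attendance before handling time, or an exposure statement that is too high for the first pair. Neither alters the design, the sample size or the analysis.

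The conclusion rests on three points: the primary rating is taken at insertion, lens order is randomized, and the wear time is stated only approximately. It also allows for the redacted V2 steps, which may or may not contain a wear window. Sections 4.1.2, 4.3.1, 4.4.1 and 6 must be reconciled as an editorial matter, and the sponsor is the one who can say which figure was intended. Whichever it is, no result or conclusion of the trial would be expected to differ.
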